**Rhythm Experience and Africana Culture Trial
(REACT)
NCT Number: NCT03771716**

Approved Protocol

Last Updated: August 29th, 2023

1.0 **SUMMARY:**

African Americans are almost two times more likely than whites (i.e., Caucasians) to experience Alzheimer's disease or other forms of dementia (1). Higher prevalence translates to 45% higher Medicare costs for African Americans compared to whites (2). A critical public health question emerges from these statistics that we intend to address in this study: Is there an effective method for reducing or eliminating the race disparities in cognitive and brain health?

Fortunately, physical activity (PA) interventions may be effective at improving neurocognitive function and reducing risk for dementia. Despite these promising results, prior PA interventions have had few African Americans making it difficult to stratify results by race to determine whether African Americans respond to PA in a similar manner and magnitude as whites. In addition, the terms 'physical activity' and 'exercise' are often considered unpleasant, painful, and fatiguing, which can negatively influence interest, enrollment, and long-term adherence to PA interventions.

Here, we propose an innovative and culturally sensitive method of increasing PA in older (60-80 yrs.) African Americans. We will conduct a ***randomized intervention*** where 180 older African Americans are assigned to either a moderate intensity ***African Dance*** group 3 days per week (N=90) or to an ***Africana Culture*** group 3 days per week (N=90) for 6-months. Both before and at the completion of the intervention, we will collect a comprehensive neuropsychological battery, physiological health metrics, and MRI metrics of brain health and function to identify biological pathways by which PA influences neurocognitive health in an African American population.

We have assembled a highly creative, productive, and interdisciplinary team with a long history of collaboration and experience conducting exercise interventions in older adults to test the following aims:

Aim 1. Examine whether a 6-month African Dance intervention improves cognitive performance compared to the culture control group. H1: The dance group will show cognitive improvements in a domain-specific fashion such that executive and memory functions will be enhanced more than other cognitive domains.

Aim 2. Examine whether African Dance influences brain morphology, task-evoked neural responses, cerebral blood flow, and resting state connectivity. H1: We predict that African Dance will increase volume, white matter integrity, perfusion, and functional activation/connectivity in a regionally-specific fashion such that prefrontal and hippocampal areas will be more sensitive to the intervention than other brain regions.

Aim 3. Explore potential physiological and socioemotional mechanisms of the dance intervention. We will collect measures of physical and psychosocial health such as waist circumference, blood pressure, blood glucose and lipid levels, mood, anxiety, depression, and loneliness and examine whether intervention-related changes to these measures mediate improvements in cognitive performance.

1.1 BACKGROUND AND RATIONALE:

1.1.1 Health Disparities and Age-Related Neurocognitive Decline.

When compared to whites, African Americans are 2-3 times more likely to develop dementia (1, 3). Such striking health disparities do not appear to be driven by genetic factors but by increased rates of vascular diseases, obesity, and hypertension in African Americans (4-6). *Despite such remarkable disparities, African Americans are routinely underrepresented in both longitudinal studies and clinically randomized trials for prevention or treatment of cognitive decline.*

Cognitive performance typically declines across the adult lifespan with executive and inhibitory control processes, working memory, and episodic memory displaying early and disproportionate decline (7). Brain atrophy precedes cognitive decline in a graded fashion with prefrontal and medial temporal lobes showing earlier and more rapid decline (8-10). Although the biological bases for these changes remain unclear, cardiometabolic risk factors predict and possibly contribute to accelerated loss (11, 12). For example, our group demonstrated that obesity is associated with diffuse reductions in white matter integrity (13).

Increased prevalence of vascular and metabolic risk factors in African Americans is thought to contribute to their increased risk for neurocognitive deficits (4, 5, 14). For example, 72% of African Americans over the age of 55 have high blood pressure compared to 54.0% of whites (15) and, after adjusting for age, 46.55% of African Americans meet criteria for obesity compared to 33.8% of whites (16). Because of elevated vascular risks in African Americans, decline in brain integrity and function may occur earlier in the lifespan than for whites (10, 12, 17). As such, *interventions that target cardiovascular health in African Americans could have significant consequences on neurocognitive function.*

1.1.2 Physical Activity (PA) Restores Brain Function. PA has emerged as a promising, low-cost method for improving neurocognitive function in older adults (18-21). Prospective epidemiological studies indicate that physical inactivity is a significant risk factor for dementia and potentially contributes to 21% (over 1.1 million) of AD cases in the US (22). Randomized interventions have shown restorative effects of PA on cognitive and brain outcomes in older adults (18, 20). For example, moderate intensity exercise, in the form of brisk walking, improves cognitive function in as little as 3-months, primarily in domains of executive function and memory (23). In addition, our research group has found that higher fit adults have larger hippocampal volumes than less fit counterparts (24) and that a one-year walking intervention reverses age-related atrophy of the hippocampus (18). Our research has also found that walking about 1 mile per day was sufficient to spare gray matter volume in prefrontal and hippocampal areas and that greater volume in these regions cut the risk of cognitive impairment in half (25). These changes have downstream effects on brain function. For example, we have demonstrated increased activity in prefrontal and parietal regions during inhibitory control after 6-months of exercise training (26). Furthermore, we

found that exercise training increased functional brain connectivity between the posterior cingulate and hippocampal and frontal medial cortices relative to the control group (27).

There are three important take-home messages from this research: 1.) *Diminution*: a sedentary lifestyle leads to cognitive and brain decline, 2.) *Plasticity*: the brain remains modifiable throughout the lifespan and PA has the capacity to take advantage of this property, 3.) *Intervention*: PA interventions enhance brain integrity. Despite these well-established principles, evidence for all of them comes from studies with predominantly Caucasian participants, even though African Americans could equally gain from such an intervention.

1.1.3 Dancing as a method for increasing PA. Dancing is an engaging form of PA that attracts cross-generational groups of all races and ethnicities. In particular, older adults prefer activities involving music, which is why dance is often used in senior centers and nursing homes as a therapeutic tool to elevate activity (28). Randomized interventions have demonstrated that dancing is effective at increasing PA and improving physical fitness. For example, traditional ballroom, tango, or salsa, improves mobility, balance, motor skills and coordination, and resting heart rate in older adults (29, 30). Dancing also improves self-confidence, motor skills, mood (31) and cognitive function (e.g., 32) while epidemiological studies find that dancing reduces risk for cognitive impairment (33). Preliminary data from our lab suggests that dancing also improves balance, gait, and cognitive function (34).

African Dance refers to a loose constellation of dance practices derived from Africa. In part because of the large African diasporic population in the US, African Dance is surging in popularity in many cities and has helped revitalize the roots and traditions of African culture by educating both the black and white communities in African heritage. African dance differs from almost all other dance cultures in one primary way. Whereas in the majority of dancing around the world the body is treated as a single “block,” in African dance the body has multiple, semi-independent centers (35). In African dance, the torso, shoulders, pelvis, and legs are relatively independent – each region of the body follows a different rhythm and gestural pattern. Because of African dance’s “polycentricity” (35), total body articulation is heightened and therefore requires significant movement, coordination, and endurance. Hence, African Dance is engaging while also being a moderately intense form of PA. *In sum, African Dance is an effective and engaging method of increasing PA and is culturally sensitive and appealing to an African American community (see below for preliminary data).*

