1.2.1 Effects of exercise on cognitive function: Our group was one of the first to demonstrate the favorable effects of a 6-month aerobic exercise RCT on cognitive outcomes (39, 10). In a meta-analysis of 18 RCTs in older adults, we found that exercise broadly influenced cognitive function (Hedge's $g=.47$), but improved executive function more than other cognitive domains (Hedge's $g=.67$), with the largest effect sizes for study durations of 6 months or longer (23). These encouraging effects have now been replicated by our group and others (18, 27, 40). **Implications:** We have significant experience conducting PA interventions. Our results demonstrate that >6-months of PA improves cognitive function and that we have been successful at recruiting and retaining older adults in PA intervention trials.

1.2.2 Effects of exercise on brain outcomes: Our research group has published >100 papers on the effects of exercise and fitness on brain morphology, white matter integrity, resting state connectivity, and task-evoked functional MRI activity. In 120 cognitively normal adults between 60-80 yrs of age (N=60/group), moderate intensity exercise was effective at increasing hippocampal volume, which was correlated with improvements in spatial memory (18). In addition to brain

morphology, changes in cardiorespiratory fitness resulting from an exercise RCT were correlated with increased white matter integrity in PFC and temporal lobes in 70 cognitively normal adults (41). Our results also extend to resting-state connectivity and task-evoked activation. For example, in 65 cognitively normal older adults exercise increased functional connectivity (27) and these changes were correlated with improvements in executive function, memory, and increases in serum BDNF and IGF-1 (37). *Implications for this project:* Our team is well-versed in the methods, challenges, and analytical approaches for examining MRI outcomes in PA interventions. We have been successful in coordinating neuroimaging efforts across sites and maintaining participants in MRI studies that are >1 year in duration.

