1.3.1 General Approach. We will analyze data in an intent-to-treat (ITT) manner such that all participants, regardless of whether they complete the intervention, will be invited to return for the follow-up sessions and will be included in primary analyses. Secondary analyses will be conducted using a per-protocol approach, which restricts the analysis to the participants that completed the intervention. All cognitive and neuroimaging data will be interrogated for normality, and symmetry, and any non-normal data may be transformed based on the distribution of error terms. Any data that cannot be transformed will be analyzed using non-parametric tests. Non-parametric regression models will be used for continuous variables when necessary. We will examine the data for potential outliers. If it is determined that outliers are due to misreporting of data or administrative error, we will delete them from the analysis. If the outliers are not due to misreporting of data or administrative error we will conduct the analysis with and without outliers included. Outlier de-weighting will be conducted on voxel-wise MRI data to remove the influence of anomalous voxels in the analysis. All analyses will be two-tailed. We will first summarize baseline demographic and brain characteristics of the sample and intervention groups using descriptive statistics and statistical hypothesis testing. Descriptive statistics will include mean, median, standard deviation, range for continuous variables, and frequency for categorical variables. Statistical tests will be conducted using t-test, ANOVA F-test, Chi-square test, correlations (Pearson or Spearman) as appropriate. Our primary goals are to examine whether the intervention improves cognitive and brain health. To test these hypotheses, we propose to use a General Linear Mixed Model (GLMM) in standard neuroimaging and statistical packages. Effects of Time (baseline, 6-month), Group (Dance, Education), and Time by Group interactions will be examined. Post-hoc comparisons using least square means will decompose any significant interactions and will be plotted to illustrate the direction of the effect. Mean differences between groups for all cognitive and neuroimaging outcome measures will be derived using linear contrasts and multiple comparisons will be corrected by standard protocols. Differences in baseline characteristics will be accounted for by using covariance

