- History of severe head trauma, major stroke, or brain tumors

- History of psychiatric disorders other than past major depressive episodes or anxiety
- History of falls or other balance problems
- History of heart or cardiovascular disease, including heart failure, angina, or hypertension not currently controlled by medication (i.e., exceeding 190/100).
- Unable to complete submaximal fitness test

1.7.3 Baseline Testing.

There are several outcome measurement sessions at baseline (Cognitive, Fitness/Blood, and MRI sessions) which must be completed prior to randomization. It will be recommended that all assessments happen within a 6-week window that starts the day the informed consent document is signed at session 1. However, given challenges with scheduling and safety clearances that may be necessary in older adults, we will work to collect all baseline data on participants, even if the session exceeds the 6-week window.

Session 1: Participants will come to the laboratory and complete a battery of cognitive and neuropsychological tests (see below for a description of the tests). Compliance with the test instructions will be monitored by a study certified administrator. Participants will be allowed to take breaks between tests on a regular basis to help reduce fatigue. The cognitive tasks to be completed during the cognitive session are described in more detail below. The tasks can be grouped into several broad cognitive categories:

- *General Cognition:*
 1. MOCA (Montreal Cognitive Assessment): was designed as a rapid screening instrument for mild cognitive dysfunction. It assesses different cognitive domains: attention and concentration, executive functions, memory, language, visuoconstructional skills, conceptual thinking, calculations, and orientation. Time to administer the MoCA is approximately 10 minutes. The total possible score is 30 points; a score of 26 or above is considered normal.
 2. Wechsler Test of Adult Reading (WTAR): estimates pre-morbid intellectual functioning (approximate intelligence). This test takes approximately 5 minutes to administer and will only be administered at the baseline testing session.
- *Working Memory:*

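### Aim 1 predicts a larger effect in executive and memory domains than in others, but no planned analysis compares effects between domains (Aim 2's regional clause has the same gap, at lower priority)

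*Combined protocol and SAP*

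**What the plan says.** In the protocol Summary, the H1 under Aim 1 is domain-specific: the dance group should improve "such that executive and memory functions will be enhanced more than other cognitive domains". The H1 under Aim 2 has the same form for the brain: "prefrontal and hippocampal areas will be more sensitive to the intervention than other brain regions".

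The analysis is described in protocol section 1.3.1 and again in the SAP (Power and Statistical Analysis). Both name a mixed model with Time, Group and their interaction. Least-squares means are used to decompose significant interactions. Both add: "Mean differences between groups for all cognitive and neuroimaging outcome measures will be derived using linear contrasts". On multiplicity, the two texts go no further than to say that "multiple comparisons will be corrected by standard protocols". Section 1.11 names executive functioning and hippocampal volume as the primary outcomes and says that each imaging outcome is first analysed on its own.

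For cognition, section 1.3.3 and the SAP give more than 91% power at d = 0.70 with 65 per arm, and describe this as power for the primary hypotheses. For brain volume, section 1.3.4 and the SAP give 81% at d = 0.50. The closing note of the SAP reduces the target from 180 to 150 participants.

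**The concern.** Each H1 asserts that one treatment effect exceeds another. Testing that requires a comparison of effects across domains or across regions. A Time-by-Group test on a single outcome shows whether dance beats the culture class on that outcome. It does not show whether the benefit is larger there than elsewhere.

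Followed as written, the plan gives no answer to the pattern prediction, and any rule for judging specificity would have to be chosen once results are known. The power statement adds to the difficulty: because it refers to the primary hypotheses, a reader could take it to cover the between-domain difference.

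**Working it through.** **Is there a test anywhere?** The candidates, taken in turn:

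- The linear contrasts are between groups, for each measure. They do not compare measures.
- The post-hoc least-squares means decompose terms already in the model, and the model has no Domain or Region term.
- The optional hierarchical regression in section 1.11 ranks imaging measures as explanations of cognitive improvement. It does not compare how regions respond to dance.
- Voxel-wise maps show where an effect passes a threshold, not that it is larger there than elsewhere.
- The interaction terms described later in section 1.3.1 and in the SAP belong to exploratory regressions run without regard to assigned group.
- Multiplicity correction controls error over the tests that are run. It does not add one.

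None of these supplies the comparison.

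**The plan's own power figures.** Inputs: 65 per arm; d = 0.70 and d = 0.50; two-sided testing (section 1.3.1). The alpha level is not stated, so 0.05 is assumed. Formula: noncentral t with 2n − 2 degrees of freedom and noncentrality d√(n/2).

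- d = 0.70: noncentrality 0.70 × √32.5 = 3.99, power 97.7%. The stated >91% is true as a lower bound.
- d = 0.50: noncentrality 0.50 × √32.5 = 2.85, power 80.8%. The stated 81% is reproduced.

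Each uses one effect size on one outcome. Neither contains a gap between domains or a correlation between domains.

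**What a between-domain contrast would have.** Scale each domain's change to unit SD and assume a common correlation r between domain changes. The mean of k1 target domains minus the mean of k2 comparator domains has variance (1 − r)(1/k1 + 1/k2). The standardised effect is therefore

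e = gap / √[(1 − r)(1/k1 + 1/k2)],

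and power follows from the noncentral t as above, with e in place of d.

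- Gap: section 1.2.1 reports that exercise "improved executive function more than other cognitive domains", with g = 0.67 for executive function and 0.47 for cognition broadly. The difference is 0.67 − 0.47 = 0.20.
- Correlation: not in the documents; 0.3 to 0.7 is assumed.
- Sample size: 65 per arm as planned. For 150 randomised, assume 75 per arm and the same retention: 65/90 = 72%, and 0.722 × 75 = 54 per arm.

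Example, executive function against the mean of three domains with r = 0.3: √[0.7 × (1 + 1/3)] = 0.966; e = 0.20/0.966 = 0.207; noncentrality 0.207 × √32.5 = 1.18; power 21.6%.

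| Contrast, gap 0.20 | 65 per arm, r 0.3 to 0.7 | 54 per arm, r 0.3 to 0.7 |
|---|---|---|
| Executive v one comparator | 16.0% to 30.9% | 14.0% to 26.5% |
| Executive v mean of three | 21.6% to 43.2% | 18.7% to 37.0% |
| Three targets v three comparators | 38.1% to 71.6% | 32.6% to 63.4% |

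The third row assumes the 0.20 gap for every target domain. Section 1.2.1 supports it, at most, for executive function, because no memory effect is given there. In the other direction, the 0.47 may itself include executive tasks, so the gap from the remaining domains could exceed 0.20. At an assumed gap of 0.30, executive function against one comparator has 30% to 59% power at 65 per arm.

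No figure is computed for Aim 2, because no regional effects are given.

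**The case against.** The strongest reply is that the confirmatory part of the trial is intact. The aims ask whether dance improves cognition against the culture class and whether it influences brain measures, and Time-by-Group tests on the named primary outcomes address that. This stands. It confines the point to one clause of each H1, and for Aim 2 it leaves little more than a labelling matter.

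A second reply is that the domains are not obscure. Section 1.7.3 says "The tasks can be grouped into several broad cognitive categories" and lists tests under domain headings, while section 1.1.1 singles out "executive and inhibitory control processes, working memory, and episodic memory displaying early and disproportionate decline". This also stands in part: likely target and comparator sets can be read off. They are nevertheless not assigned to H1, and naming the sets would not by itself create a test.

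Three stronger readings are tempting and are not supported. A reader might infer that the primary efficacy tests are compromised; they are not. A reader might infer that specificity will be claimed when one domain is significant and another is not; the plan states no such rule. A reader might infer from the table that the contrast is underpowered; the gap of 0.20 is borrowed from a meta-analysis that compared executive function with cognition broadly, and the documents give no effect for targets minus comparators.

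**Conclusion.** The comparative clause of Aim 1 H1 has no planned test, and it should have one or be relabelled. The regional clause of Aim 2 H1 has the same gap with lower priority. The absence of a test rests on the text alone and needs no numerical assumption.

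The >91% and 81% figures are sound for single outcomes at 65 per arm and say nothing about differences between domains. How far power for the contrast would differ from them depends on the true gap, the correlation between changes and the number of domains averaged. The tabulated values, from 14% to 72%, hold for a 0.20 gap in units of the SD of change, two-sided alpha 0.05, equal SDs and a common correlation. They show that a separate power statement is needed, not what its result will be.

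**What to change.** **Aim 1.** Before outcomes are analysed by group:

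- Assign the section 1.7.3 headings to target and comparator sets. The text points to executive function, working memory and episodic memory against processing speed, visuospatial and language. The investigators should confirm where working memory belongs.
- Add one Group × Time × Domain contrast on domain scores standardised by the pooled baseline SD, secondary to the Time-by-Group test of executive functioning.
- State its power with the assumed gap and the assumed correlation between domain changes. The calculation above uses SD-of-change units, so a gap expressed in baseline SDs must be converted first.

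**Aim 2.** Label the regional clause exploratory. Alternatively, add a Group × Time × Region contrast only for a modality whose target and comparator regions are named in advance, such as volume.

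**Both.** State beside the >91% and 81% figures that they apply to single-outcome tests.

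The cost is SAP wording, the domain definitions and one extra model on data already being collected; for Aim 2 it is wording only if the clause is labelled exploratory. There are two downsides. Power for the contrast may be well below the single-outcome figures. Unequal reliability of the domain scores can also produce a small gap by itself, so a significant contrast would still need cautious reading.
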